6.3.3. Per Protocol Population

All participants in the total vaccinated population with no major protocol deviations that are determined to potentially interfere with the immunogenicity assessment of the study vaccine for the relevant time point, were seronegative for the relevant HPV type at baseline, and have a valid serology result for the relevant time point. This population will serve as the primary analysis population for the immunogenicity endpoints. The population will be adapted by time point to include all eligible subjects' data up to the time of the disqualifying protocol deviation.

The criteria for exclusion of participants from the Per Protocol Population will be based on the review of protocol deviations at a Data Review Meeting (DRM) attended by the sponsor, investigator, and CRO representatives.

6.4. Covariates and Subgroups

All safety analyses will be presented by group, site, and overall. All immunogenicity analyses will include adjustment for site. A sensitivity analyses of all immunogenicity data with an adjustment for baseline concentration or titer on the log scale will be conducted if 10% or more subjects are seropositive at baseline. Additionally, if 10% or more subjects are seropositive at baseline descriptive summaries of immune response among baseline seropositive and seronegative subjects will be generated.

6.5. Missing Data and Outliers

All attempts will be made to collect all data per protocol. Missing safety data will not be imputed and only observed data collected from participants and available in the appropriate study population will be used for analysis.

The analysis of immunogenicity will be performed primarily on the PP set. Missing immunogenicity data will not be imputed.

6.6. Interim Analysis and Data Monitoring

6.6.1. Interim Analysis

Upon collection, shipment, and laboratory analysis of the Month 7 serology sample from the subjects in the 0, 6 Cecolin[®] and Gardasil[®] arms (i.e., vaccination groups 1 and 4), an interim analysis will be initiated. The interim analysis will include the analysis of the primary and secondary immunogenicity endpoints for groups 1 and 4 and the analysis of all available secondary safety endpoints for these two groups. A DRM will assess protocol deviations for groups 1 and 4 up to month 7. Only the sponsor will receive the report generated by Emmes, and will receive the following tables, figures, and listings:

• Tables 3-16, 18-23, 26-29, 31-38, 46-51, 55-63, 65-67, 74-77, 79-81 83-106, Figures 9-12, and Listings 8, 10, 11, 15, 20, 21.

6.6.2. Protocol Safety Review Team (PSRT)

The PSRT will be comprised of site Principal Investigators, PATH Medical Officer and CRO medical monitor who will routinely monitor safety throughout the duration of the trial.

A separate document will detail the mock table shells, listings and figures to be reviewed by the PSRT.

6.6.3. Data and Safety Monitoring Board (DSMB)

The PATH DSMB will convene prior to study initiation and then at least every six months prior to and following the interim analysis to examine the accumulated safety and enrollment data, review study progress, and discuss other factors (internal or external to the study) that might impact continuation of the study as designed.

In addition to routinely scheduled calls, if the PSRT has serious safety concerns or study pause criteria are met, the PATH DSMB will convene by teleconference to jointly review the data. The PATH DSMB

reviews will be summarized with recommendations to the study Sponsor as to whether there are safety concerns and whether the study should continue without change, be modified, or be terminated.

A separate document will detail the mock table shells, listings and figures to be included in DSMB reports.

6.7. Multiple Center Studies

There are 2 sites in this study. All safety and immunogenicity results will be presented by site and overall. Statistical analyses of immunogenicity results will include adjustment for trial site.

6.8. Multiple Comparisons/Multiplicity

The primary objective includes three non-inferiority comparisons of Cecolin[®] at 0 and 6 months, 0 and 12 months, and 0 and 24 months with Gardasil[®] at 0 and 6 months. To control the type I error rate for the three co-primary non-inferiority hypotheses, a Bonferroni correction resulting in a one-sided alpha of 0.0083 and corresponding to 98.3% confidence intervals (CI) will be used.

No other adjustments for type I error rate will be made.

7. STUDY SUBJECTS

7.1. Disposition of Subjects

Table 3 will present a summary of the reasons that subjects were screened but not enrolled. The composition of analysis populations, by study group and visit (for immunogenicity), will be presented separately for the Total Vaccination and Per Protocol Populations (Table 4, Table 7, and Table 10). Summaries will also be generated by site. The disposition of subjects and receipt of study vaccinations will be tabulated by study group for all subjects. Summary of subject disposition will include number of subjects screened, randomized, receiving study product, completing the study, and with immunogenicity results available (Table 13). A CONSORT diagram of the study will also be prepared (Figure 1, Appendix B). A summary of visit attendance will be prepared, along with vaccine administration and blood collection (Table 16).

A listing of subjects who discontinued vaccinations or terminated from study follow-up and the reason will be included in Listing 1, Appendix C. Further, a listing of visit completion status by subject will be prepared (Listing 2).

7.2. **Protocol Deviations**

A summary of subject-specific protocol deviations will be presented by the deviation category, deviation type, and study group for all subjects (Table 17). All subject-specific protocol deviations and non-subject-specific protocol deviations will be included as data listings (Listing 3 and Listing 4). Protocol deviations will not necessarily always lead to exclusion from the Immunology analysis population.

7.3. Demographic and Other Baseline Characteristics

A summary table of continuous measures (age, height, weight) and categorical measures (race) will be presented overall, by treatment group and by site (Table 18, Table 19 and Table 20). Descriptive statistics will be supplemented with two-sided level $\alpha = 0.05$ statistical assessment of differences between groups, using Fisher's exact test for categorical variables, and the Kruskal-Wallis test for continuous variables. This table will also be repeated for the per-protocol population, overall and by site (Table 21, Table 22, and Table 23). Demographic listing will also be prepared (Listing 5).

7.3.1. Prior and Concurrent Medical Conditions

All current illnesses and past pre-existing medical conditions will be MedDRA[®] coded using MedDRA dictionary version 20.1 or higher. Summaries of subjects' pre-existing medical conditions will be prepared (Table 24), and individual subject listings will be prepared for all pre-existing medical conditions (Listing 6).

7.3.2. Prior and Concomitant Medications

Concomitant medications will be coded to the Anatomical Therapeutic Classification (ATC) using the WHO Drug Dictionary. The use of prior and concomitant medications taken during the study will be recorded on the CRFs. The concomitant medications used during the 7 days post vaccination after any dose, after dose 1 and after dose 2 will be summarized by ATC level 1 and level 4 within level 1, and by study group for the total vaccinated population (Table 25). Additional by subject listings of prior and concomitant medications (administered within the 30 days after vaccination) (Listing 19) and administered after any SAE occurring during the study period (Listing 20) will be prepared. Listings will

be generated of all vaccinations administered prior to the first dose (Vaccination History: Listing 7) and for all non-study vaccines administered during the study (Listing 8).

7.4. Measurements of Treatment Compliance

A summary of the number of doses of study product administered to subjects will be prepared as part of the subject disposition table (Table 13). Vaccine administration details will be listed (Table 16, Listing 9).

8. IMMUNOGENICITY EVALUATION

The primary immunogenicity assessments will be assessed using the per protocol population. Supplementary analyses will be conducted in the total vaccinated population. For all immunological assays with predefined limits of quantitation, percentiles, and bootstrap based confidence intervals (CIs) which achieve the LLOQ or ULOQ will be replaced with "<LLOQ" or ">ULOQ", as appropriate. Analysis of immunological assays will be supplemented by reverse cumulative distribution (RCD) curves with each group for a given visit displayed on the same plot, with different panels for different visits. Assay values <LLOQ will be replaced by LLOQ/2 and values achieving the ULOQ will use the ULOQ as the observed data point in each analysis, except in analyses incorporating left and/or right censoring, in which case all values <LLOQ or >ULOQ will be censored at LLOQ and ULOQ, respectively.

GMC/T, GMC/T ratio, and corresponding confidence limits of the log-scale coefficients will be calculated using SAS PROC GLM with the LSMEANS statement of the log-scale coefficients which will be back-transformed in order to compute the estimate and corresponding confidence limits on the original scale. All models will use the log-transformed concentrations as the dependent variable, treatment group as the explanatory variable, and trial center as a covariate. All GMC/T ratios will be computed using the Cecolin containing arm as the numerator.

The GMC/T ratio and corresponding two-sided 98.3% CI for each comparison will be computed separately for each comparison to Gardasil® 0,6. Sensitivity analyses will be performed for application in the total vaccinated cohort utilizing SAS PROC LIFEREG, incorporating censoring where appropriate at LLOQ and ULOQ, and a Normal error distribution on the log scale, and adjustment for baseline concertation or titer on the log scale if 10% or more observations are censored.

A listing of all immunogenicity results is provided in Listing 10 and Listing 11.

8.1. **Primary Immunogenicity Analysis**

The primary objective of this study is to demonstrate the non-inferiority of Cecolin® administered on 0, 6-month; 0, 12-month; and 0, 24-month two-dose regimens, to Gardasil® using a 0, 6-month two-dose regimen, based on HPV Immunoglobulin G (IgG) antibody levels measured one month after the last dose for HPV types 16 and 18. Non-inferiority will be achieved if the lower bound of the 98.3% CI for the GMC ratio is > 0.5.

Anti-HPV 16 and 18 IgG antibody GMC and corresponding 95% CIs, measured by ELISA at baseline and one month after the second dose for the two-dose Cecolin® and Gardasil® arms will be summarized. These results will be supplemented with a 95% CI for the median (Table 26). GMC summaries will be repeated for each trial center (Table 27 and Table 28).

The GMC ratios and corresponding two-sided 98.3% CI for each comparison of a Cecolin® arm to the Gardasil® 0-6 arm will be computed at one month after the second dose (Table 29). The GMC ratios and CIs will also be presented in a figure along with the non-inferiority margin (Figure 2).

Graphs displaying the GMC will be created, displaying all visit numbers and treatment groups, including overlaid data points as well as error bars denoting the 95% CI, using the appropriate log scale for the y-axis (Figure 3 and Figure 4).

The analyses will be repeated as sensitivity analyses based on the total vaccinated cohort utilizing SAS PROC LIFEREG (Table 40 and Table 41).

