Based on the safety and immunogenicity data, a 60-mcg dose formulation, containing 40 mcg of HPV 16 L1 VLPs and 20 mcg of HPV 18 L1 VLPs, was planned for further efficacy trials.

A separate Phase 2 trial of the Cecolin® was a single-center, age-stratified immune-bridging study (ClinicalTrials.gov, NCT02562508) conducted in China. A total of 979 participants were enrolled to evaluate whether the immunogenicity of girls aged 9–17 years receiving 3 doses (day 0, month 1 (day 28–60) (n=453) and month 6 (day 150–240)) or girls aged 9–14 years receiving 2 doses (at months 0 and 6)) (n=301) was non-inferior to that in women aged 18–26 years receiving 3 doses (at months 0, 1 and 6) (n=225). Most of the reported adverse events in the participating girls and women were mild, and none of the SAEs reported were vaccine related. Two antibody indexes, IgG antibody and neutralizing antibody, were measured. For both antibody indexes and for both HPV-16 and HPV-18, the antibody levels in girls aged 9–17 years receiving 3 doses and girls aged 9–14 years receiving 2 doses were higher than and noninferior to those in women receiving 3 doses. The GMT ratios were similar to the three licensed HPV vaccines. Additionally, in the 3-dose groups, noninferiority at month 6 was established in girls compared with women, further verifying the data at month 7.

In this study a total of 57.6% (564/979) of the study participants reported adverse reactions, and only 1.2% (12/979) were judged as grade 3 or more severe. The most frequently reported symptoms, with occurrence rates of more than 10% in at least one study group, were pain, fever and cough, among which all but 2 were mild, at grade 1 or 2. Three participants reported serious adverse events (SAEs) during the study (from day 0 to month 7), and none of them were considered vaccine-related. In the ages 9-14 year old, there were 163 solicited AEs reported (54.2%) in two dose group and 190 solicited AEs (61.4%) in the three dose group, most of them were mild in nature.

In conclusion, the immunogenicity of the E. coli-expressed candidate HPV bivalent vaccine in girls aged 9–17 years receiving 3 doses or girls aged 9–14 years receiving 2 doses is non-inferior to that in women aged 18–26 years receiving 3 doses.

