3.3. Study Definitions and Derived Variables

Definitions and Derivations Used in This Study:

- A baseline value will be defined as the last value obtained prior to the first vaccination of study product.
- Age will be calculated from the date of first vaccination and will be presented in whole years.
- Fever: temperature $\geq 38.0^{\circ}$ C or 100.4° F.
- For immunology, reciprocal endpoint titers less than the lower limit of quantitation (LLOQ) of the assay will be assigned a value of half the starting dilution, and those greater than the upper limit of quantitation (ULOQ) will be assigned a value equal to the ULOQ for computational purposes, except when using analysis methods that incorporate censoring.
- Seroconversion will be defined as a 4-fold rise in anti-HPV 16 and 18 IgG antibody (as measured by ELISA) compared to the baseline titer.
- Seropositive will be defined as a titer value for the ELISA assay of > 8 EU/mL for HPV-16 and >7EU/mL for HPV-18. For the PBNA assay, any IC₅₀ titers that are \geq 21 (HPV-16) or \geq 16 (HPV-18) will be considered as positive titers.

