4.3. Selection of Study Population

4.3.1. Description of Study Population

The study population will include approximately 1025 girls (205 per arm) 9-14 years of age. The study will have two sites recruited from one country in Africa (Ghana) and one country in South/Southeast Asia (Bangladesh).

Final eligibility determination will depend on the results of the medical history, clinical examination, fulfillment of all the inclusion and absence of any of the exclusion criteria, and appropriate understanding of the study and completion of the consent process by parents of all participants and assent of adolescent participants.

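### The primary GMC model adjusts for trial center only; age at first vaccination, known for every girl, could be prespecified as a covariate for a small and possibly near-zero gain

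*SAP*

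**What the plan says.** The primary model is in SAP section 8: log concentration is the outcome, with "treatment group as the explanatory variable, and trial center as a covariate". SAP section 6.4 sets the same policy: "All immunogenicity analyses will include adjustment for site". SAP section 6.7 and Protocol section 11.5.1.1 name no further covariate for the main analysis. The only other adjustment foreseen is a sensitivity analysis "with an adjustment for baseline concentration or titer on the log scale will be conducted if 10% or more subjects are seropositive at baseline", together with the censored-data sensitivity model in SAP section 8, which can also carry baseline level.

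Age is available. SAP section 3.3 states: "Age will be calculated from the date of first vaccination and will be presented in whole years". Its planned use is descriptive, with a between-group test. SAP section 7.3 says: "A summary table of continuous measures (age, height, weight) and categorical measures (race) will be presented overall, by treatment group and by site". Age enters no immunogenicity model, subgroup or sensitivity analysis. Randomization is stratified by site only (SAP section 4.4.2).

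The only antibody data by age are in Protocol section 1.5.2. Levels in girls aged 9-17 (three doses) and girls aged 9-14 (two doses) "were higher than and noninferior to those in women receiving 3 doses"; the women were aged 18-26.

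**The concern.** A baseline variable that predicts the outcome can be put in the model for one degree of freedom. If it does predict, the residual variance falls, the confidence interval for the ratio narrows, and chance differences between arms in that variable are removed. Age is a natural candidate here: it is recorded on everyone, and neither the stratification nor the model balances it.

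Baseline antibody level cannot do the same work in the primary population, since every girl in it is seronegative for the type in question.

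A second reason is the structure of the primary population. The per-protocol set requires no disqualifying deviation and a valid result at the relevant visit, and that visit is at Month 7, 13 or 25 depending on the arm. Baseline seronegativity is fixed before vaccination and does not by itself disturb the randomized comparison. Deviations and missing samples arise afterwards, over follow-up of different length, and could be related to age. Protocol section 11.6 treats missing immunogenicity data as missing at random, and conditioning on age makes that somewhat easier to accept.

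**Working it through.** **Inputs from SAP sections 5 and 6.8:** SD 0.65 on the log10 scale; margin 0.5, so log10(2) = 0.3010; one-sided alpha 0.025/3 = 0.0083; 95% power per serotype; 10% seropositive at baseline; 15% dropout; 205 per arm.

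**Assumptions, because the documents give no figure:** a true ratio of 1 or 0.9; independence of the two serotypes when their powers are multiplied; R², the share of residual variance that age explains, between 0 and 10%.

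**Step 1: the plan's own figure.** n = 2 × 0.65² × (2.394 + 1.645)² / 0.3010² = 152.1, so 153 evaluable per arm. Inflated, 153/(0.90 × 0.85) = 200 and 153/0.75 = 204. The stated 205 reproduces. With 205 × 0.90 × 0.85 = 156.8 evaluable, noncentral t power is 95.4% per serotype, and 0.954² gives about 91.1% for both.

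**Step 2: what R² might be.** If ages are uniform over the six whole years 9 to 14, Var(age) = 35/12 = 2.917. For a slope b in log10 GMC per year, R² = b² × 2.917 / 0.65².

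| Fall in GMC per year | b (absolute) | R² |
|---|---|---|
| 5% | 0.0223 | 0.3% |
| 10% | 0.0458 | 1.5% |
| 15% | 0.0706 | 3.4% |
| 20% | 0.0969 | 6.5% |

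An R² of 10% would need a fall of about 24% per year, which leaves the GMC at age 14 at about a quarter of that at age 9.

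**Step 3: effect on precision and power.** Residual SD = 0.65 × √(1 − R²); SE = SD × √(2/156.8); 98.3% half-width = 2.394 × SE. Power is from the noncentral t with noncentrality [log10(ratio) + 0.3010]/SE.

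| R² | Residual SD | Half-width, log10 (fold) | Power per serotype / both, ratio 1 | Power per serotype / both, ratio 0.9 |
|---|---|---|---|---|
| 0 | 0.650 | 0.176 (1.50) | 95.4% / 91.1% | 85.7% / 73.5% |
| 0.3% | 0.649 | 0.175 (1.50) | 95.5% / 91.2% | 85.8% / 73.7% |
| 1.5% | 0.645 | 0.174 (1.49) | 95.7% / 91.6% | 86.3% / 74.5% |
| 5% | 0.634 | 0.171 (1.48) | 96.4% / 92.9% | 87.6% / 76.8% |
| 10% | 0.617 | 0.167 (1.47) | 97.2% / 94.5% | 89.5% / 80.1% |

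**Step 4: chance imbalance.** With a 10% fall per year, the SD of the shift in the log10 ratio caused by chance age differences is 0.0458 × √2.917 × √(2/156.8) = 0.009, or about 2% on the ratio. The half-width is 0.176.

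**The case against.** The strongest case against acting is that nothing is broken. The model adjusts for exactly the factor used in stratification, the ratio is unbiased under randomization, and the sample size is met without age. Chance imbalance is tiny beside the interval width, and SAP section 7.3 would show it in both populations. All of this stands, and it is why the point is an option and not a defect.

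A reader might infer from Protocol section 1.5.2 that the trial's own background shows age to predict antibody level in this population. It does not. The contrast is between girls and adult women, and for the two-dose girls the number of doses differs as well. The three-dose girls do share the women's dose count, which makes age plausible as a predictor, but no gradient within 9-14 years is reported. The size of any gain therefore rests on an assumed R², and a range that starts above zero would overstate it: a 5-10% fall per year gives only 0.3-1.5%.

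A reader might also infer that age adjustment would repair low power at ratios below 1. It would not. At a true ratio of 0.8, power for both serotypes is about 42% without age and about 49% even at R² = 10%.

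Timing is a fair objection too. The Group 1 versus Group 4 primary comparison is reported to the sponsor at the Month 7 interim (SAP section 6.6.1) of an open-label trial, and Protocol sections 11.1 and 11.5 require the SAP to be final before then. Changing the primary model after that report would cost credibility.

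**Conclusion.** The point holds as a low-priority improvement. The primary model omits an available baseline variable that may plausibly predict the outcome. The omission neither biases the ratio under randomization nor undermines the planned size.

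Over R² of 0-10%, per-serotype power rises by 0 to 1.8 percentage points at ratio 1 (95.4% to 97.2%) and by 0 to 3.8 at ratio 0.9 (85.7% to 89.5%). The lower part of that range is as credible as the upper, so the gain may be near zero. These figures rest on the SAP's SD and attrition rates, on ages uniform over 9-14 where a slope is converted to R², and on a true ratio that the documents do not state.

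The protection against age-related loss in the per-protocol sets cannot be sized from the documents. Nor would baseline age adjust for girls in the 0, 12-month and 0, 24-month arms being older at dose two; that belongs to the regimens being compared.

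**What to change.** Before the Month 7 interim analysis, add age at first vaccination (continuous, in years) beside trial center in the GMC and GMT ratio models of SAP section 8. Use the same model at interim and final, and report the center-only ratio as supportive. SAP section 3.3 presents age in whole years, so the SAP should state that the covariate is the unrounded value.

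The documents do not say whether the interim has taken place. If its results have been seen, keep the center-only model as primary and add the age-adjusted ratio as a sensitivity analysis, labelled as specified after the interim.

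The cost is one model term, one degree of freedom out of roughly 310 in a two-arm comparison, and one supportive table. No new data are needed.

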8.2. Secondary Immunogenicity Analyses

The secondary objective is to further evaluate immunogenicity of Cecolin® and Gardasil® based on HPV IgG antibody levels and to evaluate immunogenicity based on PBNA.

The primary summary of the anti-HPV 16 and 18 IgG antibody GMC and corresponding 95% CIs, measured by ELISA will be further extended to all time points and to the mixed dose arm (Table 26). GMC summaries and seropositivity rates will be repeated for each trial center (Table 27 and Table 28).

The GMC ratio and corresponding two-sided 95% CI for the 0,6 Gardasil[®] arm compared to the 0,24 mixed dose arm at one month post-second dose (Visit 6) will be calculated to assess immunogenicity of the mixed dose arm. Additionally, the GMC ratio and corresponding two-sided 95% CI for the 0,6 Gardasil[®] arm compared to the 0,6 Cecolin[®] arm at twenty-four months post-dose one (Visit 7) will be calculated to assess persistence (Table 30).

Seroconversion in anti-HPV 16 and 18 IgG antibody, defined as a 4-fold rise from baseline, will be summarized by frequency and percentage of participants per treatment group at one month after the second dose. The difference in the percentages will be computed between the Cecolin® and mixed arms compared to the Gardasil® arm one month after the second dose with a corresponding 95% CI computed via the Miettinen and Nurminen score method (Table 31). Seroconversion summaries will be repeated for each trial center (Table 32 and Table 33).

Anti-HPV 16 and 18 serum neutralizing antibody GMTs measured by PBNA and corresponding 95% CIs, will be summarized by time point and treatment group. These results will be supplemented with a 95% CI for the median (Table 35). GMT summaries will be repeated for each trial center (Table 36 and Table 37).

Graphs displaying the GMT will be created, displaying all visits and treatment groups, including overlaid data points as well as error bars denoting the 95% CI, using the appropriate log scale for the y-axis (Figure 5 and Figure 6).

Seroconversion in anti-HPV 16 and 18 measured by PBNA will be analyzed the same as anti-HPV 16 and 18 IgG antibody (Table 38).

Correlation between neutralizing antibody titers measured by PBNA and IgG antibody concentrations measured by ELISA will be summarized on the continuous scale for anti-HPV 16 and 18 and the following three categories Cecolin only, Gardasil only, and the mixed arm with colors identify timepoints (Figure 7 and Figure 8). The Spearman correlation between ELISA and PBNA results will be computed by type and for Cecolin only, Gardasil only, and the mixed arm. Summaries will be provided by three categories Cecolin only, Gardasil only, and the mixed arm and HPV type (Table 39).

Analysis of immunological assays will be supplemented by reverse cumulative distribution (RCD) curves for each treatment group for a given visit displayed on the same plot, and different panels for different visit (Figure 9 through Figure 12). Log concentration/titer will be on the x-axis and cumulative percent will be on the y-axis.

The analyses for GMC/T and GMC/T ratio will be repeated as a sensitivity analyses based on the total vaccinated cohort utilizing SAS PROC LIFEREG (Table 42 through Table 45).

